7.8.1. Standard of Care Medications	Subjects are allowed to enter the study with a maximum of 1 SOC medication for neuropathic pain (consistent with regional or local standard of care guidelines for DPNP) that has been taken at a stable dose (defined as < 50% change in total dose) for approximately 4 weeks prior to Screening. Allowed SOC medications include: duloxetine, pregabalin, and gabapentin, amitriptyline, and venlafaxine. Attempts should be made to maintain the stable dose of SOC therapy. If changes to the dose are necessary, the Investigator should discuss with the Medical Monitor. However, dose level should not be above the maximum prescribed dose as instructed in the medication's dosage and administration section of the prescribing information. Subjects who failed to respond or tolerate SOC (approved medications for DPNP) and are receiving alternative pain medications, or are treatment naïve, are also allowed.	Amitriptyline and venlafaxine are excluded as these medications are not FDA approved for DPNP  To specify that the stable dose of the standard of care drug taken must be within the maximum dose of the drug's prescribing information  Treatment naïve patients are not allowed
7.8.2. Allowed Medications	
 
SRI for depression, subject is anticipated to be on a stable dose 3 months prior to entry and it will not change during the study;
 
Analgesics that are non-opioid, non-sedative and do not interfere with subject's pain reporting., see Section 7.8.3.
 
	To clarify the allowed stable dose
7.8.3. Rescue Medication	This does not exclude the use of these rescue medications in other forms for other uses outside of DPNP. Subjects taking one form of rescue medication can take a medication containing the other form solely for use outside of DPNP. The daily maximum dosages are inclusive of those used outside of DPNP. Subjects should be encouraged NOT to take cough syrups or sleep aids containing NSAIDs (eg, Nyquil for cold/flu, or Tylenol PM for sleep), but if they do then it should be recorded as concomitant medication.  NSAIDs taken for cardiovascular health are allowed and should be documented as a concomitant medication. The daily maximum dosages of each medication should still be maintained.	Allowing the use of NSAIDs or acetaminophen in other forms outside of treating DPNP symptoms
7.8.4. Prohibited Medications	Tricyclic antidepressants (other than amitriptyline) and other tricyclic drugs including cyclobenzaprine and promethazine; triptans (prescribed usage outside of DPNP allowed); 5-HT3 receptor antagonists;	Amitriptyline is no longer allowed  To allow the usage of Triptans for causes other than DPNP

Section	Version 2	Rationale
7.8.4. Prohibited Medications	Strong or moderate CYP3A4 inhibitors or inducers and P-gp inhibitors;	To prohibit the use of P-gp inhibitors based on DDI study data
7.8.4. Prohibited Medications	Muscle relaxers.	To prohibit the use of muscle relaxers as this is a confounding factor for pain improvement
8.1.1. Blinded Sample Size Recalculation	8.1.1. Blinded Sample Size Recalculation In order to maintain sufficient study power to detect the prespecified treatment effect for the primary efficacy endpoint (i.e., change from baseline in NPRS of 1.2 points) a sample size recalculation may be performed to evaluate on a blinded basis the study assumptions (variability and drop-out rate) used to calculate sample size. A Sample Size Recalculation Committee (SRC), comprised of Sponsor personnel and the study's blinded statistician, will be established to recalculate sample size based on blinded assessment of study assumptions. The SRC will review available data (e.g., baseline characteristics, study drug discontinuations, variability in NPRS change from baseline) when approximately 70% of the subjects have been enrolled in the study. The Sponsor may increase the sample size of the study up to 468 subjects. There will be no sample size decrease under this procedure. An increase of sample size within this range will be documented in a Note-to-File (NTF) to the Investigators and IRBs (as appropriate) and will not require a protocol amendment. Because these analyses will be based on pooled, blinded data they will not impact the Type I error rate. A Blinded Sample Size Recalculation Plan will present details regarding the planned recalculation of sample size.	To include a blinded sample size recalculation to maintain the study assumptions for variability and dropout rate and detect the effect for primary efficacy endpoint.
8.2.1. Intent to Treat Analysis Set (ITT)	The intent-to-treat (ITT) analysis set is defined as all enrolled randomized subjects categorized by their randomized treatment group (whether they received study drug).	To clarify the ITT population includes randomized patients

TEAE	treatment-emergent adverse event
TENS	transcutaneous electrical nerve stimulation

Product: RTA 901 (BIIB143)Statistical Analysis PlanStudy: 901-C-2102Version: 1.0

1. Introduction

Study 901-C-2102 is a 2-part, randomized, placebo-controlled, double-blind, Phase 2 study to evaluate the safety, tolerability, efficacy, of RTA 901 in qualified subjects with diabetic peripheral neuropathic pain (DPNP). Approximately 192 eligible subjects (64 subjects per treatment arm) will be enrolled in Part 1. Randomization within each part will be stratified by SOC pain medication using randomization and trial supply management (RTSM). The doses for Part 2 will be selected based on Part 1 data. Potential changes with study design for Part 2 may also apply pending the Part 1 results.

The purpose of this Statistical Analysis Plan (SAP) is to describe the planned analyses for Part 1 safety, tolerability, efficacy, of RTA 901 up to the Part 1 end of study visit (Week 16). A separate statistical analysis plan will be prepared for Part 2.

This SAP is based on Version 4 of the protocol, dated 9 MAY 2024. All references to the protocol refer to Version 4. This SAP will cover the planned analysis only for Part 1.

2. Study Overview

2.1. Study Objectives and Endpoints

Study Primary Objectives

Efficacy:

 To assess the efficacy of RTA 901 based on change from baseline in the average daily pain intensity score using the Numeric Pain Rating Scale (NPRS) after 12 weeks of treatment

Safety:

 To assess the safety and tolerability of RTA 901 during and following the Treatment Period

Study Primary Endpoints

Efficacy:

 Change from baseline in the average daily NPRS pain intensity score during Week 12

Safety

Frequency, intensity, and relationship to study drug of adverse events and serious
adverse events and change from baseline in the following assessment: physical
examinations, vital sign measurement, electrocardiograms, clinical laboratory
measurements, and body weight.

[figure not shown]
Study Secondary Objectives

 To assess the efficacy of RTA 901 in achieving at least 30% decrease in the NPRS pain intensity score after 12 weeks of treatment

- To assess the efficacy of RTA 901 in achieving at least 50% decrease in the NPRS pain intensity score after 12 weeks of treatment
- To assess the percentage of subjects using rescue medication for diabetic peripheral neuropathic pain (DPNP) treatment during the Treatment Period, as well as the quantity and timing of such medication use during the Treatment Period
- To assess the Daily Sleep Interference Scale (DSIS) score after 12 weeks of treatment

Study Secondary Endpoints

- Proportion of subjects who achieve at least a 30% decrease from baseline in the Week 12 average NPRS pain intensity score
- Proportion of subjects who achieve at least a 50% decrease from baseline in the Week 12 average NPRS pain intensity score
- Proportion of subjects using rescue medication for DPNP, as well as the quantity and timing of such medication use during the Treatment Period
- Change from baseline in the average DSIS score during Week 12

[figure not shown]

2.2. Study Design

Study 901-C-2101 is a 2-part, randomized, placebo-controlled, double-blind, Phase 2 study to evaluate the safety, tolerability, efficacy, of RTA 901 in qualified subjects with DPNP.

Part 1 of the study includes screening period of up to 2 weeks, a run-in period of 2 weeks, a treatment period of 12 weeks and a safety follow-up period of 4 weeks (see Figure 1). Approximately 192 subjects in Part 1 who remain eligible (according to Randomization eligibility criteria) will be randomized 1:1:1 to either RTA 901 (10 or 80 mg) or placebo at Day 1 and stratified by SOC pain medication (duloxetine or pregabalin/gabapentin).

2.3. Schedule of Activities

Table 1 Schedule of Assessments

Study Period	Screening Period ^a	Run-in Period ^b		Treatment Period						Follow-up Period	
Study Visit	Screening	Run-in	Day 1 ^c	Week 1	Week 2	Week 4	Week 6	Week 8	Week 10	Week 12 / EOT	Week 16 / EOS ^d
Study Day	Day -28 to -15	Day-14 to 1 (± 2)	Day 1	Day 8 (± 2)	Day 15 (± 2)	Day 29 (± 2)	Day 43 (± 2)	Day 57 (± 2)	Day 71 (± 2)	Day 85 (± 2)	Day 113 (± 2)
Administrative Procedures:											
Informed Consent	X										
Run-in Inclusion/Exclusion ^e	X	X									
Demographics	X										
Medical History	X										
Prior and Concomitant Medications	X	X	X	X	X	X	X	X	X	X	X
Adverse Events ^f	X	X	X	X	X	X	X	X	X	X	X
Electronic Diary Set-up	X										
Clinical Procedures/Assessments:											
Height Measurement ^g	X										
Weight Measurementh	X	X	X	X	X	X	X	X	X	X	X
Comprehensive Physical Examination	X		X							X	X
Targeted Physical Examination ¹		X		X	X	X	X	X	X		
ECG	X		X ^j	X						X	X
Vital Sign Measurements	X	X	X	X	X	X	X	X	X	X	X
MNSI	X										
Laboratory Procedures/Assessments:											
Pregnancy Tests for Females of Childbearing Potential ^k	X		X	X	X	X	X	X	X	X	X
FSH ¹	X										
Serology (Hepatitis and HIV Screening)	X										
COVID-19 Test	X		X								
Drug of Abuse and Cotinine Screen	X										

Study Period	Screening Period ^a	Run-in Period ^b		Treatment Period					Follow-up Period		
Study Visit	Screening	Run-in	Day 1 ^c	Week 1	Week 2	Week 4	Week 6	Week 8	Week 10	Week 12 / EOT	Week 16 / EOS ^d
Study Day	Day -28 to -15	Day-14 to 1 (± 2)	Day 1	Day 8 (± 2)	Day 15 (± 2)	Day 29 (± 2)	Day 43 (± 2)	Day 57 (± 2)	Day 71 (± 2)	Day 85 (± 2)	Day 113 (± 2)
Clinical Chemistry	X		X	X	X	X	X	X	X	X	X
INR	X		X	X	X	X	X	X	X	X	X
Hematology	X		X	X	X	X	X	X	X	X	X
Urinalysis and Microscopy	X		X	X	X	X	X	X	X	X	X
HbA1c	X					X		X		X	X
Fasting Lipid Profile ⁿ	X					X		X		X	X
Study Drug Procedures:											
Randomization Inclusion/Exclusion			X								
Randomization			X								
Dispense Study Drug		X	X			X		X			
Study Drug Administration ^o		X	Xp	X	X	X	X	X	X	X	
Collect / Review Study Drug			X			X		X		X	
Patient Reported Outcome Assessments:											
NPRS ^q	X	X	X	X	X	X	X	X	X	X	X
DSIS ^r	X	X	X	X	X	X	X	X	X	X	X

Abbreviations:

DSIS=Daily Sleep Interference Scale;

ECG=electrocardiogram; EOS=end of study; EOT=end of treatment;

; FSH=follicle-stimulating hormone; HbA1c=Hemoglobin A1c; INR=International

Normalized Ratio; IRB=Institutional Review Board; MNSI=Michigan Neuropathy Screening Instrument;

NPRS=Numeric Pain Rating Scale;

- a The Screening Period includes 1 clinic visit up to 2 weeks prior to the Run-in Period (within approximately 28 days prior to Day 1), see Section 3.2 of the study protocol
- b The Run-in Period includes 1 clinic visit and must occur during a 14 (± 2) day period prior to the Day 1 first dose, see Section 3.3 of the study protocol.
- c Day 1 includes the first dose administration, and all procedures must be performed before study drug administration, except for adverse events, 1-hour postdose ECG,
- d Subjects who discontinue study drug early for any reason should complete the procedures associated with the Week 12/EOT visit at the nearest study visit and the Follow-up Week 16/EOS visit 4 weeks later
- e Run-in eligibility procedures do not need to be repeated at the Run-in visit; however, a review of any changes in eligibility criteria should be evaluated prior to Run-in visit procedures.
- f Adverse event assessments should be performed after the informed consent has been signed.
- g Height should be measured with no shoes.
- h Weight should be measured with no shoes, hats, or outerwear.
- i Investigator will evaluate if a targeted physical examination is needed, based on any symptomatology reported to the study team.
- ECG on Day 1 should be recorded at predose and 1-hour postdose.
- k A serum pregnancy test will be performed at Screening for females of child-bearing potential or at any point in time if a pregnancy is suspected. All other pregnancy assessments will be urine pregnancy tests. Additional pregnancy assessments will be performed more frequently if required by local law or requested by local regulatory authorities or IRBs.
- 1 FSH will only be assessed at Screening for female subjects who have been post-menopausal for at least 1 year and are not surgically sterile.
- n Subjects should fast for at least 8 hours prior to clinic visits where fasting lipids are taken (Screening, Week 4, Week 8, Week 12, and Week 16).
- o All study drug administration should be performed in an early fasted state, defined as having no food within at least 2 hours prior to study drug administration and for 1 hour following study drug administration. Since the first dose will be taken in-clinic and there are no fasting lipids taken at the Run-in visit, subjects should fast for 2 hours prior to the visit.
- p On visits containing both labs with fasting and study drug administration, the longer fasting guidance (8 hours) is to be followed, these are not additive.
- q Subjects will complete the NPRS in the e-diary daily at bedtime.
- r Subjects will complete the DSIS in the e-diary daily upon waking.

2.4. Sample Size Considerations

This sample size for Part 1 is based on a dose-ranging scheme to evaluate initial safety, efficacy, of RTA 901 in patients with DPNP. The primary comparisons for efficacy are between each of the 2 RTA 901 treatment groups and the placebo treatment group. With assumed treatment difference of 1.2 and standard deviation of 2.4 in NPRS pain intensity, 64 subjects per arm approximately provides 80% power with two-sided alpha of 0.05. The purpose of Part 1 is to provide dose selection information for Part 2.

3. Definitions

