#### 1.4. Dose Rationale

In summary, at the proposed doses for Part 1, RTA 901 is predicted to have efficacious and safe exposure in subjects with DPNP, with a 10 mg dose anticipated to be an efficacious dose and 80 mg the highest feasible dose with potentially maximal efficacy and an acceptable safety profile. However, based on the exposures associated with efficacy in the nonclinical models, it is possible that a dose lower than 10 mg may need to be explored to identify the minimally effective dose in subjects with DPNP and thereby enable a robust phase 2 dose ranging study. Therefore, a planned E-R analysis for efficacy from the all subjects in Part 1 of this study will be incorporated to recommend the optimal doses for investigation in Part 2. Eligible doses for selection in Part 2 will be limited to a dose range of 1 to 80 mg. Part 2 doses will not exceed 80 mg, at which there is at least a 40-fold safety margin based on the data from the 3-month GLP toxicity studies in mice and monkeys.

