### 8. STATISTICS

### 8.1. Sample Size Estimate

This study will be conducted in 2 parts. A total of approximately 192 subjects (64 subjects per treatment arm) are planned for randomization in Part 1 and approximately 192 subjects (64 subjects per treatment arm) are planned for randomization in Part 2, for a total of 384 subjects to be randomized. This sample size is based on a dose-ranging scheme to evaluate initial safety, efficacy, of RTA 901 in this population. The primary comparisons for efficacy are between each of the 2 RTA 901 treatment groups and the placebo treatment group. The overall Type I error rate will be controlled at the 0.05 significance level. A hierarchical testing strategy to control the overall Type I error will be defined in the SAP. Power calculations are based on a 2-sample t-test with no adjustments for multiple comparisons. The study assumes a difference in NPRS pain intensity means of 1.2 between each RTA 901 treatment group and the placebo treatment group and a standard deviation of 2.4.

If doses selected for Part 2 do not include doses studied in Part 1, then an analysis by dose group for Part 1 or Part 2 doses will be performed following completion of each study part. Within each Part, with 64 subjects per treatment group, each study part has 80% power to compare treatment groups to placebo.

If doses selected for Part 2 include any doses studied in Part 1 (ie, 10 or 80 mg), then an analysis by dose group will be performed using Part 1 and Part 2 combined, following completion of the study. The dose group that is enrolled in both parts will have 128 subjects. With 128 placebo subjects compared to 128 subjects in the RTA 901 dose group, there is 98% power to detect the same difference (1.2 NPRS points) assuming the same standard deviation (2.4). RTA 901 dose groups that are enrolled in only 1 part will have 64 subjects. With 128 placebo subjects compared to 64 subjects in each RTA 901 dose group, there is 90% power to detect the same difference (1.2 NPRS points) assuming the same standard deviation (2.4).

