6.2. Multiplicity Control

A sequential stepwise testing will be performed on the primary endpoint for RTA 901 group (80mg, 10mg) compared to placebo in the following testing order to control the overall type I error at two-sided alpha level of 0.05:

- Step 1: Comparison of 80 mg group versus placebo group. If p-value <0.05, then proceed to Step 2. If not, testing for subsequent step is considered as exploratory.
- Step 2: Comparison of 10 mg group versus placebo group.

No formal testing will be performed for the secondary endpoints.

6.3. Primary endpoint of change from baseline in NPRS average pain intensity at week 12

The primary endpoint is the change from baseline in the average daily NPRS pain intensity score during Week 12.

The NPRS of pain intensity is a numeric scale, ranging from 0 (representing no pain at all) to 10 (representing the worst pain imaginable). The subject selects a whole number (0 to 10) that best indicates the intensity of their neuropathic pain in the past 24 hours. Subjects will report how they perceive their average neuropathic pain intensity during the past 24 hours at bedtime.

The weekly mean is defined as the sum of non-missing daily scores divided by the number of days with non-missing scores for that week. Subjects with fewer than 3 daily scores during an analysis week will be considered to have a missing weekly average for that week.

No imputation will be conducted at weekly mean level.

The MMRM model will include baseline NPRS score, visit, treatment, the interaction of treatment and visit, the interaction of baseline NPRS score and visit. The analysis visit will include all visits (study week) up to week 12 during double-blinded treatment period. An unstructured covariance (UN) matrix will be used to model the within-subject variability. Model convergence will be checked. If the unstructured covariance model fails to converge with the Newton-Raphson algorithm after increasing the default maximum iterations, the Fisher scoring algorithm will be used to provide initial values of the covariance parameters.

If the model does not converge with an unstructured covariance matrix, then the analysis visit will include weeks 1, 2, 4, 6, 8, 10 and 12 per protocol scheduled assessment visits.

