In the event that none of the above methods yield convergence, the following covariance structures are substituted, in the order listed. Each subsequent covariance structure is used only if each previous covariance structure is used, and no previous model converged.

- 1. Heterogeneous Toeplitz covariance structure (assuming different variances at each time point and that measurements taken closer together in time are more highly correlated than those taken farther apart).
- 2. Toeplitz covariance structure (assuming measurements taken closer together in time are more highly correlated than those taken farther apart).
- 3. First order auto-regressive [AR(1)] covariance structure (assuming measurements taken closer together in time are more highly correlated than those taken farther apart, but the correlation is more constrained than the Toeplitz structure).
- Compound symmetry covariance structure (assuming equal correlation for measurements from a patient, regardless of how far apart in time they were taken). A compound symmetry covariance structure was assumed in the sample size calculation.

The corresponding plots will also be generated. The primary inference will be based on the treatment comparison at Week 12. The LS means with standard errors of each dose level at each visit as well as of treatment differences between the RTA 901 group (10 mg, 80 mg) vs. placebo at each visit will be presented, along with 95% CI and p-value at each visit.

Descriptive statistics for observed data, including NPRS score and change from baseline in the NPRS weekly average scores, will be evaluated by treatment group and visit (including EOS visit) with descriptive statistics (mean, SD, median, 1st and 3rd quartiles, range) in the ITT population.

The change from baseline of weekly average NPRS score will also be analyzed for the perprotocol population using the same MMRM model as for the ITT population as a sensitivity analysis.

A sensitivity analysis will be performed excluding any data after a subject discontinued randomized study treatment.

Product: RTA 901 (BIIB143) Statistical Analysis Plan Study: 901-C-2102 Version: 1.0

An MMRM model including all post-randomization visits up to Week 16 will be performed as sensitivity analysis.

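### Does the 80% power in SAP 2.4 overstate the chance of formal success on 10 mg under the fixed testing sequence?

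*SAP*

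**What the plan says.** SAP 2.4 first names the comparisons, "The primary comparisons for efficacy are between each of the 2 RTA 901 treatment groups and the placebo treatment group". For a difference of 1.2 and an SD of 2.4 it then states that "64 subjects per arm approximately provides 80% power with two-sided alpha of 0.05". It adds that Part 1 exists to inform dose selection for Part 2.

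Protocol 8.1 gives the basis: "Power calculations are based on a 2-sample t-test with no adjustments for multiple comparisons". It assumes the same effect at both doses: "The study assumes a difference in NPRS pain intensity means of 1.2 between each RTA 901 treatment group and the placebo treatment group". It leaves the testing hierarchy to the SAP.

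SAP 6.2 sets that hierarchy: "Step 1: Comparison of 80 mg group versus placebo group. If p-value <0.05, then proceed to Step 2". If Step 1 fails, the 10 mg test is exploratory.

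Two statements in SAP 6.3 also bear on the calculation. On missing weekly scores: "No imputation will be conducted at weekly mean level". In the list of fallback covariance structures: "A compound symmetry covariance structure was assumed in the sample size calculation".

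**The concern.** Three things look wrong on a first reading.

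- **The gate.** SAP 2.4 calls both doses primary and attaches a single 80% to them. Under SAP 6.2, formal success on 10 mg needs two significant tests, so its power must be below 80%. SAP 2.4 omits the protocol's remark about multiplicity and does not name the test.
- **Missing data.** The t-test needs 63.8 subjects per arm for 80%, so 64 leaves no margin for a missing Week 12 mean.
- **The basis.** The protocol cites a 2-sample t-test, while SAP 6.3 says compound symmetry entered the calculation.

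What would be at stake is the reading of a 10 mg result. Someone relying on SAP 2.4 alone could overrate the chance of a formal 10 mg claim by about 11 percentage points, and could be surprised by a nominally significant 10 mg result that ranks only as exploratory.

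**Working it through.** **Inputs.** Difference 1.2 and SD 2.4, two-sided 0.05, 64 per arm (SAP 2.4); the same 1.2 for each dose (protocol 8.1); 1:1:1 allocation with one placebo arm (SAP 2.2); order 80 mg then 10 mg (SAP 6.2).

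**1. The plan's own figure.** The variance of a difference in means is 2 × 2.4² / 64 = 0.18, so the SE is 0.424 and the noncentrality is 1.2 / 0.424 = 2.83. The two-sided t-test with 126 df has power 80.1% (80.7% by normal approximation). The figure reproduces. So do the protocol's other two: 128 vs 128 gives 97.9% (stated 98%) and 64 vs 128 gives 90.1% (stated 90%).

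**2. Power through the gate.** With equal arms and a shared placebo the two test statistics have correlation 0.5. Formal success on 10 mg is P(both significant).

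- Bivariate normal, both means 2.83, critical value 1.96: 69.7%.
- Simulation of 1,000,000 trials: 69.0% with pairwise variances, 69.3% with variance pooled over three arms.
- 10 mg significant but 80 mg not: 80.1% − 69.0% ≈ 11%.

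Power for 80 mg stays at 80.1%, because a fixed sequence spends no alpha before its first step.

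**3. Dependence on the assumed effects** (complete data):

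| 80 mg effect | 10 mg effect | 10 mg singly | 10 mg through the gate |
|---|---|---|---|
| 1.2 | 1.2 | 80% | 69% |
| 1.4 | 1.2 | 80% | 76% |
| 1.6 | 1.2 | 80% | 79% |
| 1.2 | 1.0 | 65% | 58% |

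Protocol 1.4 describes "80 mg the highest feasible dose with potentially maximal efficacy", so the rows with a larger 80 mg effect are at least as plausible as the equal-effects row.

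**4. Missing Week 12 data.** The current documents give no rate, so these are assumptions. On an unadjusted t-test with effects of 1.2:

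| Missing | Evaluable per arm | 80 mg | 10 mg through the gate |
|---|---|---|---|
| 10% | 64 × 0.90 = 57.6 | 75.8% | 63.1% |
| 15% | 64 × 0.85 = 54.4 | 73.4% | 59.9% |
| 20% | 64 × 0.80 = 51.2 | 70.7% | 56.6% |

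The primary analysis is an MMRM with baseline as covariate. If 2.4 is an unadjusted SD (not stated), the residual SD is 2.4 × √(1 − r²) for baseline correlation r:

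- r = 0.3, 10% missing: SD 2.29; power 79.6% for 80 mg and 68.2% for gated 10 mg.
- r = 0.5, 15% missing: SD 2.08; power 84.7% and 75.4%.

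Under these assumed values the covariate roughly offsets the loss or more than offsets it.

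**5. Compound symmetry against t-test.** With complete data and treatment-by-visit terms, leaving aside the baseline covariate, the Week 12 contrast under compound symmetry is the difference in Week 12 means. Its variance is 2 × SD² / n = 0.18, the same as in step 1. Both descriptions can lead to 64 per arm.

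**The case for a change.** The best case for a change is that the SAP was the first document able to give power under the sequence. The protocol deferred the order and named the SAP as final arbiter of the analyses, so its power statement should stand on its own. The equal 1.2-point effect is the protocol's own assumption, so 69% uses the plan's inputs. The repair would be two or three sentences in SAP 2.4 and a line in SAP 6.3.

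Part of this stands. SAP 2.4 does not name the t-test or repeat that multiplicity is ignored; neither document gives the 69%; no missing-data allowance is stated; and SAP 6.3 does not say how compound symmetry was used.

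The rest does not carry. SAP 2.4 identifies each dose versus placebo in the sentence just before the figure, so the single-comparison reading is there. The protocol on which the SAP is based discloses the test and the lack of adjustment, and SAP 6.2 states the gate plainly. Power for each comparison taken singly is a legitimate basis for sizing a dose-ranging part; power for passing both tests is an additional operating characteristic that authors may report or leave out. Nor could a new sentence affect sizing: SAP 6.1 already cites how many randomized patients take duloxetine, so it was written with randomization data in hand.

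**Conclusion.** The concern does not call for a change. The 80% in SAP 2.4 is right for each dose taken singly, and it is the formal power for 80 mg. Formal power for 10 mg through the gate is about 69% if both doses have a 1.2-point effect with SD 2.4 and 64 evaluable per arm; it runs from 58% to 79% over the other effects examined. The missing-data loss rests on assumed rates that baseline adjustment may offset, so a net shortfall is not shown. The compound-symmetry sentence is unexplained but compatible with the t-test result.

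No decision turns on any of this. Protocol 4.5.2.3 bases the Part 2 doses on the exposure-response analysis of all Part 1 subjects, and SAP 6.3 reports the 10 mg difference with its confidence interval and p-value whatever happens at Step 1. Adding the joint figure would label a correct number more fully, but enrolment, the analysis and the conclusions would stay as they are. A reader interpreting a gated-out 10 mg result can apply the 69% and its range directly.
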